## 5.2. Participant Accountability

The number (and percentage) of subjects screened, screening failure, randomized, withdrew prior to dosing, dosed, completed treatment, discontinued treatment and the reasons for discontinuation from treatment, completed the study, withdrew the study and reason for withdrawal will be summarized in a table.

If there are any subjects who discontinued from treatment or withdrew from study due to reasons associated with the COVID-19 pandemic or reasons associated with humanitarian emergencies, a separate summary will be presented to summarize these reasons.

A listing of subjects who discontinued treatment/withdrew from study and the associated reasons for discontinuation/withdrawal will be presented. Two separate listings will also be presented for subjects who discontinued treatment/withdrew from study due to the COVID-19 pandemic or to humanitarian emergencies if applicable.

## 5.3. Demographic and Baseline Characteristics

Baseline data (demography, medical history, SMA history, and baseline disease characteristics) will be summarized.

Formal statistical analyses will not be done to test for homogeneity between treatment groups. If there are apparent heterogeneities between the groups in any of the participant characteristics that are of clinical importance or could affect the treatment outcome, the impact of the imbalances will be investigated and, if appropriate, adjustments made in the efficacy and safety analyses.

Demography includes age at screening, age at first dose, sex, ethnicity, race and country,

Medical history will be coded in MedDRA and the number and percentage of subjects with each medical history presented by preferred term.

SMA history will include gestational age, birth weight, age at symptom onset, time from disease onset to enrollment, age at SMA diagnosis, history of SMA symptoms (hypotonia, developmental motor delay, paradoxical breathing, pneumonia or respiratory symptoms, limb weakness, swallowing or feeding difficulties, and other symptoms), and the number of copies of the SMN1 and SMN2 gene.

Baseline disease characteristics will be assessed by CHOP INTEND total score, total HINE Section 2 motor milestones, and growth parameters - these assessments are further described in Section 6. If a participant was receiving ventilation at Day 1, then the number of hours of ventilation use on Day 1 will also be summarized as baseline. In addition, use of a gastrointestinal tube will be presented. Use of gastrointestinal tube will be determined from either medical history or as a procedure prior to first dose coded as 'Gastrostomy' or 'Gastrointestinal tube insertion'.

Product: Nusinersen	Statistical Analysis Plan
Study: 232SM203	Version: 3.0 Final

Demographic and baseline disease characteristics will be presented for the ITT Set, the PPS, the Safety Set as appropriate. Additional presentations will be presented to facilitate comparisons at baseline for the planned efficacy comparisons. For example, for the primary endpoint to compare the higher dose to CS3B sham control.

## 5.4. Protocol Deviations

Protocol deviations identified during site monitoring will be captured in a protocol deviation log and categorized as major or minor deviations. These deviations will be listed. Major protocol deviations will be summarized including those that lead to exclusion from the Per protocol Set.

Participants with incorrect stratification i.e. any mismatch between the stratification used for randomization on the IRT system and the actual stratification according to the eCRF will also be listed. A separate summary of major protocol deviations related to the COVID-19 pandemic will be presented.

## 5.5. Study Treatment Exposure

The number of doses received, and the number of sham procedures performed will be displayed using frequency distributions. The cumulative amount of nusinersen received will be summarized using summary statistics.

The overall time on study will be summarized descriptively by treatment. Overall time on study will be calculated (section 3.1). The duration will also be categorized and summarized using the following categories: <29 days, >=29 to 64 days, >=64 to 99 days, >=99 to 135 days, >=135 to 183 days, >=183 to 218 days, >=218 to <260, >=260 to 302 and >=302 days

Given the long half-life of nusinersen, participants are considered to be exposed from the time the first dose of nusinersen was administered (in or before the start of study) to the date of last visit or contact.

Separate listings will be provided showing what subjects were randomized to as well as study drug administration data which will include lot numbers, actual treatment received, cumulative number of doses and cumulative doses. A listing of dosing errors will also be provided i.e. where either the incorrect dose was administered as specified in protocol deviation log and kit description from IRT system. A listing will also be presented to show whether any of the missed doses are related to COVID-19. If any of the doses are due to COVID-19, then the number of impacted doses will be presented.

# 6. Efficacy Endpoints

## 6.1. General Analysis Methods for Efficacy Endpoints

## **Multiple imputation (MI)**

Product: Nusinersen	Statistical Analysis Plan
Study: 232SM203	Version: 3.0 Final

The multiple imputation method [Schafer 1997, Schafer 1999] will be used for participants who discontinue for a reason other than death or have a missing efficacy result at the timepoint of interest. This will be performed for CHOP INTEND, HINE Section 2 total score and NF-L. Any imputation on an item level within a scale for CHOP INTEND and HINE section 2 will be performed prior to performing MI.

The imputations will be performed on total scores. All available data will be used i.e., where subjects have missed doses but continued to perform assessments; otherwise, any missing values will be imputed using MI. In a situation where historical data is used as the control group only the visits which are common between the two groups will be utilized. For example, for the CS3B sham control versus higher dose comparison only the Day 64, Day 183 and Day 302 visits will be included in the list of post baseline visits.

In this situation if convergence issues occur then only the Day 64 and Day 183 post baseline visits will be included.

The Markov Chain Monte Carlo (MCMC) method will be used to impute the missing score.

The treatment variable will be coded so that the Higher dose group is the first in the sort order. Prior to the Proc MI step the dataset will be sorted by treatment and then ascending unique subject identifier (USUBJID). The variable list in the model for imputations will include:

- treatment group, disease duration, baseline value for the endpoint, and all available post baseline values
- For NF-L, the log of baseline and post-baseline values will be used in the PROC MI step.

A set of 100 complete imputed datasets will be generated and the relative efficiency parameter will also be checked to determine the acceptability of the imputed results i.e. it should be close to 98% or higher. The seed used for the multiple imputation for CHOP INTEND will be 5846892, for HINE section 2 Motor Milestones will be 8746890 and for NF-L will be 7635789.

If the MI procedure imputes any values outside the expected range for the scale, e.g. from 0 to 64 for CHOP INTEND, then values below 0 will be set to 0 and values above 64 will be set to be 64. For NF-L if any imputed values are  $< \log(LLOQ)$  then set as  $\log(LLOQ/2)$ .

For each of the 100 imputed datasets, the endpoint will be compared between treatment groups using an ANCOVA model for continuous endpoints and logistic regression for binary endpoints as described in the main analysis for each endpoint. Additional detail such as how the joint rank test will be implemented and the adjustment for baseline covariates is described below and for each endpoint in Section 6.3 and 6.4

The estimates from the 100 fitted models will be combined to provide an overall estimate with corresponding confidence intervals and p-value using PROC MIANALYZE [Little et al, 2002].

For the continuous endpoints, the difference between treatments and the corresponding CI will be presented. For the analyses using logistic regression the odds ratio and corresponding CI will

Product: Nusinersen	Statistical Analysis Plan
Study: 232SM203	Version: 3.0 Final

be presented. In addition, the estimates of the binomial proportions in each treatment arm and the differences between treatments will be presented (Ratitch, 2013).

In the presentation of results from multiple imputed data, the number of subjects with missing data will be summarized.

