## ANCOVA model

For each of the 100 imputed datasets, the endpoint will be compared between treatment groups using an ANCOVA model for continuous endpoints (primary, secondary and NF-L endpoints). The ANCOVA model will include covariates for each of the corresponding baseline value for the endpoint, baseline CHOP INTEND total score (if not the endpoint under consideration) and disease duration at informed consent. The model will be used to present overall LS means and standard errors for each treatment group, and LS mean differences for treatment with corresponding 95% CI.

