### Main Analysis

 The change from baseline to Day 183 in Motor Milestones total score will be analyzed using the JRT methodology to account for mortality. The ANCOVA model will include covariates for baseline Total Milestone score, baseline CHOP INTEND

Page 44

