## Table 7: Change from baseline to Day 183 in Motor Milestones total score: comparison: 50/28mg versus CS3B sham control

## 6.4.3. Change in Plasma NF-L from (ratio to) baseline to Day 183: comparison: 50/28mg versus CS3B sham control.

### **Plasma Neurofilament**

The analysis will be performed on the ITT set but is it noted that neurofilament plasma samples from China sites were not analyzed due to export law complication. The baseline and post baseline results for NF-L for these participants will be imputed in the MI step.

For Plasma NF-L, if the baseline is missing than the first available assessment post dose, within Day 2, will be used instead as baseline.

Product: Nusinersen	Statistical Analysis Plan
Study: 232SM203	Version: 3.0 Final

Values that are BLQ will be set to half of the diluted LLOQ (2.6 pg/mL).

The Neurofilament light chain (NF-L) plasma concentration change (including absolute and ratio to baseline) will be presented by visit.

Summary tables and LS-mean (+- 95% CI) plots for geometric mean ratio to baseline using MI data +ANCOVA will be presented.

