### Main Analysis

The change from baseline in Plasma NF-L from (ratio to) baseline to Day 183 will be analyzed using the JRT methodology to account for mortality. The ANCOVA model will include covariates for baseline log plasma NF-L, baseline CHOP INTEND total score and disease duration at screening.
 Ranking based on death will be performed as

described earlier for CHOP INTEND. In terms of ranking based on the NF-L, progressively higher ranks will be given to subjects with a greater reduction in NF-L at Day 183.

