Square brackets in the 3rd column denotes the covariates to include in the ANCOVA/Logistic regression model. If analysis is also using multiple imputation, then these covariates will be included in the imputation step.

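### Infantile-onset SAP: the imputation model for HINE-2 and NF-L omits baseline CHOP INTEND, which the analysis model adjusts for, at some cost in precision, chiefly for NF-L

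*SAP*

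**What the plan says.** All of this is in the Part B infantile-onset SAP unless stated otherwise.

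- **Imputation.** Section 6.1, Multiple imputation (MI), says of the method: "This will be performed for CHOP INTEND, HINE Section 2 total score and NF-L". The variables are "treatment group, disease duration, baseline value for the endpoint, and all available post baseline values".
- **Analysis, general text.** Section 6.1, ANCOVA model, adjusts for the endpoint's own baseline plus "baseline CHOP INTEND total score (if not the endpoint under consideration) and disease duration at informed consent". Section 6.1, Joint rank methodology + MI, names only the endpoint baseline and disease duration.
- **Rank 3, HINE-2 at Day 183 against sham (Section 6.4.2).** "The ANCOVA model will include covariates for baseline Total Milestone score, baseline CHOP INTEND" and disease duration.
- **Rank 4, NF-L at Day 183 against sham (Section 6.4.3).** The model has "covariates for baseline log plasma NF-L, baseline CHOP INTEND total score and disease duration at screening".
- **Rank 7, NF-L at Day 64 against 12 mg (Section 6.4.6).** It follows Section 6.4.3.
- **Rank 6, HINE-2 at Day 302 against 12 mg (Section 6.4.5).** It follows Section 6.4.4, which names no covariates.
- **China sites (Sections 6.4.3 and 6.4.6).** Plasma samples for NF-L were not analysed. "The baseline and post baseline results for NF-L for these participants will be imputed in the MI step".

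For its external comparisons, the later-onset SAP (Section 5.2) says of the ANCOVA and logistic covariates: "If analysis is also using multiple imputation, then these covariates will be included in the imputation step".

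**The concern.** An imputation model should contain at least the variables of the analysis model. If it leaves one out, the imputed outcomes have no association with that covariate given the listed variables. The analysis then mixes observed values that follow the covariate with imputed values that do not. The covariate's coefficient shrinks and adjustment explains less variance.

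Baseline CHOP INTEND is not a marginal covariate in this plan. It is one of the two variables used to match the sham children (Section 6.2). The other, disease duration, is in the imputation list.

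The precision lost matters because the testing sequence in Table 2 is fixed: a miss at rank 4 ends inference for ranks 5 to 11, and a miss at rank 7 ends it for ranks 8 to 11. The plan's check on the imputations, a relative efficiency near 98% or higher, cannot show the problem. Relative efficiency is 1/(1 + λ/m) with λ the fraction of missing information, so with m = 100 it is never below 1/(1 + 1/100) = 99.0%.

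**Working it through.** **The plan's own figure.** The only design figure is at least about 99% power for CHOP INTEND, with 50 against 20, difference 24 and SD 8.8. For the functional part alone, z = 24 / (8.8 × √(1/50 + 1/20)) = 24 / 2.328 = 10.31, and 10.31 − 1.96 = 8.35, so power exceeds 0.9999. The figure is plausible. It does not bear on this point, because CHOP INTEND's own baseline is in its imputation model.

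**Which tests are affected.** MI with HINE-2 or NF-L as endpoint occurs at ranks 3, 4, 6 and 7. Rank 2 (responders) uses no MI. Ranks 3 and 4 name baseline CHOP INTEND in their own sections, and rank 7 takes it by reference. Rank 6 takes it only if the general ANCOVA text governs, not the joint-rank text.

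**What each child's imputation rests on.** A dropout has an endpoint baseline and earlier visits, which carry part of the association with CHOP INTEND. A China participant's NF-L has neither, so only treatment and disease duration remain.

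**Size, by simulation.** The NF-L-type data were in standardised units. Assumptions: correlations between CHOP INTEND, disease duration and NF-L; 10% random dropout at the last visit; 10% or 30% China; no deaths. There were 20 imputations, rank ANCOVA on treatment, endpoint baseline, CHOP INTEND and disease duration, Rubin's rules, and 500 replicates. In the sham runs the China share falls on the higher-dose arm only, and mean baseline CHOP INTEND differs by 0.3 SD between groups. Entries are without / with baseline CHOP INTEND in the imputation model; complete-data values are in brackets.

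| Scenario | CHOP INTEND coefficient | Treatment SE | Rejection rate |
|---|---|---|---|
| 50 v 25, null, 10% China | 8.04 / 9.97 (10.12) | 5.48 / 5.25 | 0.056 / 0.058 |
| 50 v 25, effect, 10% China | 7.76 / 9.58 (9.73) | 5.33 / 5.12 | 0.548 / 0.580 (0.646) |
| 50 v 25, null, 30% China | 5.89 / 9.69 (10.04) | 6.35 / 5.89 | 0.046 / 0.046 |
| 50 v 25, effect, 30% China | 5.57 / 9.42 (9.85) | 6.07 / 5.72 | 0.408 / 0.464 (0.612) |
| 50 v 25, null, dropout only | 9.38 / 9.98 (10.09) | 5.09 / 5.01 | 0.048 / 0.062 |
| 50 v 20 sham, null, 10% China | 7.74 / 9.18 (9.29) | 5.37 / 5.20 | 0.052 / 0.054 |
| 50 v 20 sham, null, 30% China | 6.15 / 8.98 (9.32) | 5.72 / 5.43 | 0.056 / 0.054 |

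From the table:

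- **Attenuation (randomised null runs):** 1 − 8.04/9.97 = 19% at 10% China, 1 − 5.89/9.69 = 39% at 30%, and 1 − 9.38/9.98 = 6% with dropout only, the pattern closest to HINE-2.
- **Treatment SE:** wider by 5.09/5.01 − 1 = 1.6% (dropout only), 5.33/5.12 − 1 = 4.1% (10% China, effect) and 6.35/5.89 − 1 = 7.8% (30% China, null).
- **Power for NF-L:** 0.580 − 0.548 = 0.032 and 0.464 − 0.408 = 0.056.
- **Type I error:** 0.046 to 0.062 over the imputed randomised null runs. The Monte Carlo SE is √(0.05 × 0.95/500) ≈ 0.010.
- **Sham comparison:** the mean null treatment difference was 0.63 without and 0.25 with CHOP INTEND (10% China), and 0.49 and −0.20 (30%). These are shifts of 0.38 and 0.69 ranks, against SEs of 5.37 and 5.72.

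**The case against.** The other side has several good points.

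- **The list may not be exhaustive.** That reading is possible. But the plan fixes seeds and sort order so that the imputation can be reproduced, so the variable list should be complete too.
- **The joint-rank text omits CHOP INTEND, so imputation and analysis agree.** This stands for rank 6 until the two general texts are reconciled, so a reader who counts four affected tests goes beyond the document. It fails for ranks 3, 4 and 7, where the endpoint sections govern and name the covariate.
- **Imputed values are not cut off from CHOP INTEND.** Correct. A reader might infer that they carry no relation to it at all. Only the part not carried by the listed variables is set to zero. The stronger statement is nearly true only for NF-L in China participants.
- **The later-onset rule is not a sponsor standard.** Also correct. It belongs to a separate SAP and to its external comparisons. That SAP's own NfL analysis adjusts for baseline HFMSE, which its imputation list (Section 5.1.1) omits. The rule shows that the practice is known, but it does not bind this plan.
- **No decision error is shown.** A reader might infer type I error inflation, or a biased sham comparison because missing NF-L is tied to the new study's sites. The rejection rates do not show inflation. Bias requires a difference in baseline function that the documents do not report. A smaller run on the mean log scale (40 replicates, assumed shifts of 0.5 and 0.8 SD) gave −1.032 and −1.055 against −0.999 with complete data. With a Monte Carlo SE of about 0.215/√40 = 0.034, these are about 1.0 and 1.6 SEs away, so that run does not establish bias.

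**Conclusion.** The mismatch is real at ranks 3, 4 and 7, and conditional at rank 6. It is a point of consistency and efficiency, not of error control. Its weight lies with NF-L at ranks 4 and 7. For HINE-2 the effect is minor: about 6% attenuation and a 1.6% wider SE in the dropout-only run. That run used the randomised 50 v 25 layout and NF-L-type data, so there is no direct figure for HINE-2 against sham.

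The sizes rest on assumed correlations, dropout, China shares of 10% to 30% and, for sham, a 0.3 SD imbalance. The document states none of these. The simulation had no deaths and used 20 imputations, not the planned 100. The SE and power figures indicate an order of magnitude only. What rests on the text alone is that the imputation model is narrower than the analysis model, and that China participants' NF-L is drawn without their known baseline function.

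**What to change.** 1. In Section 6.1, Multiple imputation (MI), add baseline CHOP INTEND total score to the variable list when the endpoint is HINE-2 total score or NF-L, and state that every ANCOVA covariate is in the imputation model.
2. Bring the covariate list in Joint rank methodology + MI into line with the ANCOVA model text and Sections 6.4.2 and 6.4.3, and name the covariates for the Day 302 HINE-2 test in Section 6.4.5.

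The cost is one variable, already collected, in PROC MI. The small downside is a slightly larger MCMC model. For the sham comparison the plan already foresees possible convergence problems and has a fallback that drops Day 302; the same fallback can be kept.

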## Joint rank methodology

Death is a potential outcome in the infantile-onset population and the joint rank methodology will be utilized to incorporate both the functional endpoint and mortality.

The joint rank methodology [Berry 2013] allows for a statistical test of the treatment effect on the endpoint while accounting for truncation of data due to deaths. In this analysis, a subject's joint rank score will be calculated by comparing each subject to every other subject in the study, resulting in a score of +1 if the outcome was better than the subject being compared, -1 if worse, and 0 if the same. The subject's score will then be calculated by summing their comparison to all the other subjects in the study.

For the purpose of this calculation, considering an endpoint for change to Day 183, subjects will be grouped into the following 2 categories:

- Group 1: Participants who complete Day 183 and have data available AND subjects who withdraw from the study due to reasons other than death and don't have Day 183 data available
- Group 2: Participants who die will be ranked based on the time of death

The criteria for withdrawals are based on withdrawal from study. A subject may discontinue treatment but still continue in the study and in this case data from assessments conducted after treatment will be included for analysis.

## Joint rank methodology + MI

MI will be used to impute all missing data including data after withdrawal from the study or where a participant completed the study but doesn't have an evaluable score at the timepoint of interest. No efficacy data would be available after death. MI will be performed as described earlier and subjects who died will be included in the MI model, but any values imputed after death will not be used for determining the rank score. Therefore, all subjects except withdrawals due to death will have a value at Day 183 (either observed or imputed). In each of the 100 imputed datasets, subjects will be ranked as follows:

- Subjects in Group 2 will be given lower ranks than subjects in Group 1, with the lowest ranks being given to the subjects who die in the shortest time after first dose. Progressively higher ranks will be given to subjects who die at longer times after first dose.
- Subjects in Group 1 will rank higher than subjects in Group 2. Progressively higher ranks will be given to subjects with a higher change in CHOP INTEND at Day 183.

Product: Nusinersen	
Study: 232SM203	

For example, for 2 subjects in Group 1 their comparison score will be based on the endpoint of Day 183 CHOP INTEND. The subject being ranked will be given a comparison score of -1 if their CHOP INTEND is worse than that of the comparison subject. If the score is the same in both subjects their comparison will be considered a tie and so a comparison score of 0 will be assigned. For subjects who do not survive, a subject who dies earlier than the comparator subject will be given a comparison score of -1. If two subjects die the same number of days from their first dose of study medication their comparison will be considered a tie i.e. comparison score of 0 will be assigned.

The subjects will be ranked according to their subject rank scores in each of the 100 MI datasets. In the instance of ties, the mean of the corresponding ranks will be assigned to the tied subjects. Hence, in general, these comparisons will result in subjects who die being assigned the worst scores and ranked according to time of death. Subjects who survive and complete the study and subjects who withdraw from the study will be ranked more favorably than subjects who die.

For each of the 100 imputed datasets, the ranked scores will be compared between treatment groups using an ANCOVA model. The ANCOVA model will include treatment as a fixed effect and adjusted for each of the corresponding baseline value for the endpoint and disease duration

The model will be used to obtain the p-value from PROC MIANALYZE for the joint rank.

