## 2.3. Sample Size Considerations

The justification for the sample size for the infantile-onset SMA population in Part B is detailed as follows.

For the purposes of sample size determination, it is assumed that the higher dose will achieve an additional 4.5 improvement in CHOP INTEND and additional 3% in survival over the 12 mg dose. For the infantile-onset SMA population in Part B, a sample size of approximately 50 participants in the 50/28 mg Group and 20 sham subjects from study CS3B will provide at least approximately 99% power for the primary endpoint to detect an improvement of 24 points

Product: Nusinersen	Statistical Analysis Plan
Study: 232SM203	Version: 3.0 Final

on CHOP INTEND and 23% survival rate benefit (compared to that observed in Study CS3B participants receiving sham control) at Day 183 based on the joint rank test at a 2 sided significance level of 0.05. This power calculation is based on simulations using data generated from a joint model of survival and functional change. The model used a difference of 24 points for the Day 183 change from baseline in CHOP INTEND total score (50/28 mg Group – Study CS3B Sham Control Group) and a population standard deviation of 8.8 for change from baseline.

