# 5. Statistical Methods for Planned Analyses

Within the infantile-onset population to control the overall type 1 error at a 2-sided alpha level of 0.05, a sequential testing procedure ranked in the order of the primary and secondary endpoints will be utilized. Table 2 summarizes the planned statistical testing. Inferential conclusions about each successive analysis require statistical significance of the prior one.

Rank	Endpoint	Comparison Higher dose to:	Population	Description
1	Change from baseline to Day 183 in CHOP-INTEND total score	CS3B Sham control	Matched Sham Set	Primary
2	Proportion of HINE Section 2 motor milestone responders at Day 183	CS3B Sham control	Matched Sham Set	Secondary
3	Change from baseline to Day 183 in HINE Section 2 total score	CS3B Sham control	Matched Sham Set	Secondary
4	Change from baseline to Day 183 in plasma NF-L	CS3B Sham control	Matched Sham Set	Secondary

 Table 2:
 Sequential Testing Procedure for Primary and Secondary endpoints

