## 5.1. General Principles

Descriptive summary statistics will be presented for all primary, secondary **continuous** endpoints collected. Unless otherwise specified, for continuous endpoints, the summary statistics will generally include number of participants with data, mean, standard deviation, median, 25th percentile, 75th percentile, minimum and maximum. For categorical endpoints, the summary statistics will generally include number of participants with data, and the percentage of those with data in each category.

All summaries and listings will be presented by study groups unless otherwise specified. Visits in listings will be displayed as per CRF data collection rather than analysis visits.

The statistical software, SAS®(Version 9.4) will be used for all summaries and statistical analyses.

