## 6.2. Use of Historical Data

The primary and some secondary endpoints will compare high dose to sham control. A total of N=37 are available from CS3B at Day 183. The following algorithm will be used to select the maximum number of Sham control subjects who are comparable at baseline to 232SM203 (N=75) based on two covariates: disease duration at informed consent, baseline CHOP INTEND total score. The algorithm will stop at a minimum of 20 participants.

[figure not shown]

[figure not shown]

Page 33

Page 34

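### The Part B plans pool 100 imputed ANCOVAs without stating complete-data degrees of freedom; run that way, the 24-participant later-onset intervals come out too short

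*SAP*

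**What the plan says.** Part B later-onset SAP, section 5.1.1: "A set of 100 complete imputed datasets will be generated", the endpoint is analysed in each dataset, and "The estimates from the 100 fitted models will be combined to provide an overall estimate with corresponding confidence intervals and p-value using PROC MIANALYZE". Section 5.1.5 applies this to HFMSE, RULM, NfL, ACEND and PedsQL. Each ANCOVA has treatment plus three covariates, in 24 participants randomised 16 to 8.

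Part B infantile-onset SAP, section 6.1, has the same pooling sentence, with "corresponding confidence intervals and p-value using PROC MIANALYZE". For the joint rank test it adds "The model will be used to obtain the p-value from PROC MIANALYZE for the joint rank". The primary comparison is sized on "approximately 50 participants in the 50/28 mg Group and 20 sham subjects from study CS3B", and section 6.2 says of the sham matching: "The algorithm will stop at a minimum of 20 participants". Section 5 sets up a fixed sequence of 11 tests "to control the overall type 1 error at a 2-sided alpha level of 0.05".

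SAS 9.4 "will be used for all summaries and statistical analyses". The plans fix the seeds, the sort order and a relative-efficiency check. Neither gives complete-data df for the pooling step. The only df rule in the two imputation sections is Satterthwaite, for the infantile-onset sensitivity analysis with separate variances by arm. Nothing says whether those df are carried into the pooled result.

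**The concern.** Rubin's df depend only on the number of imputations and on the share of information lost to missing data. They do not depend on sample size unless the complete-data df are supplied. With 100 imputations they run into the thousands, so a t distribution on 19 df gives way to the normal.

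The result is perverse: an analysis with missing data uses a smaller critical value than the same ANCOVA with none. The later-onset SAP would even contain both treatments side by side. The WHO motor milestone ANCOVA has the same number of terms but no multiple imputation, so it would be referred to t on 19 df (2.093). HFMSE, in the same children, would be referred to about 1.96. Intervals would be too short and p-values too small.

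**Working it through.** **Inputs.** m = 100 imputations (both plans). Later-onset: N = 24, with intercept, treatment and three covariates = 5 parameters, so complete-data df = 24 − 5 = 19. Infantile-onset primary: N = 70 at the matching minimum (50 + 20), with intercept, treatment and two covariates = 4 parameters, so df = 66. The 50/28 mg v 12 mg comparison: N = 75, df = 71. The largest possible primary comparison uses all 37 sham participants: N = 87, df = 83. The fraction of missing information, λ, is not in the documents; 0 to 0.30 is assumed.

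**The plan's own figure.** Section 2.3 of the infantile-onset SAP states about 99% power or more for 24 points, SD 8.8, 50 v 20. Ignoring deaths, the standard error is 8.8 × √(1/50 + 1/20) = 2.33, and 24/2.33 = 10.3, so power is essentially 100%. A joint-rank simulation (4,000 runs, assumed sham survival 55%, 65%, 75%, with the stated 23-point benefit) gave 99.8%, 100% and 100%. The stated power is reproduced.

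**Formulas.**
- Without complete-data df: ν = (m − 1)/λ² = 99/λ².
- With them (Barnard–Rubin): ν_obs = ν_com(1 − λ)(ν_com + 1)/(ν_com + 3), and 1/ν_adj = 1/ν + 1/ν_obs.
- Real error = 2 × P(t on ν_adj > critical value used).

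**Later-onset, ν_com = 19.**

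| λ | ν | value used | ν_adj | value needed | interval should be wider by | real error |
|---|---|---|---|---|---|---|
| near 0 | very large | 1.960 | 17.3 | 2.107 | 7.5% | 6.6% |
| 0.05 | 39,600 | 1.960 | 16.4 | 2.116 | 7.9% | 6.7% |
| 0.10 | 9,900 | 1.960 | 15.5 | 2.125 | 8.4% | 6.8% |
| 0.30 | 1,100 | 1.962 | 12.0 | 2.180 | 11.1% | 7.3% |

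Against plain t on 19 df the value needed is 2.093: 6.8% wider, real error 6.5%.

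**Infantile-onset.**
- Primary at N = 70 (66 df): 5.4% by plain t, rising to 5.6% at λ = 0.30; intervals should be 1.9% to 2.8% wider.
- N = 75 (71 df): 5.4% to 5.6%.
- N = 87 (83 df): 5.3% to 5.5%.

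**Simulation check.** Null data, 12,000 runs per setting, 0% to 20% missing (Monte Carlo standard error about 0.002).

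| Comparison | error without complete-data df | error with |
|---|---|---|
| 16 v 8 | 0.062–0.068 | 0.041–0.049 |
| 50 v 20 | 0.053–0.056 | 0.049–0.051 |
| 50 v 25 | 0.051–0.055 | 0.047–0.050 |

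A joint-rank null at 50 v 20 with nothing missing gave 0.053 (normal) against 0.050 (t on 66 df). Primary power stays at 99.8% or more under either reference.

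**Smaller later-onset models.** PedsQL self-report leaves out children aged 2 to 4. If 16 participants remained (an assumption), df = 11 and the real error would be 8.0% to 9.3%.

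**The case against.** The strongest objection is that the plans are silent rather than wrong. Both name PROC MIANALYZE, and EDF= is an option of that procedure, so a programmer who sets it complies with the text. The error arises only if the procedure runs with complete-data df left infinite, and no passage says that it will. This stands, and it makes the point conditional. It does not remove it: two analysts following this text could report different intervals and p-values, and the choice should not be made after unblinding.

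A reader might infer that type 1 error control in the infantile-onset sequence fails, or that the primary result is in doubt. The documents do not support either. Rank 2 is a responder analysis without multiple imputation, and ranks 8 to 11 are log-rank tests. The remaining six tests move by roughly 0.3 to 0.6 percentage points, and a comparison with about 99% power will not turn on that.

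Nor should the later-onset figure be read as a confirmatory error rate. That part has no primary efficacy endpoint and no alpha-controlled sequence, and its sample size is not statistically based.

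For the matched external comparisons, 16 v 16 (27 df) gives 6.0%, but 1:1 is the last fallback. The designs tried first give about 5.5% (16 v 48, 60 df) and 5.6% (16 v 32 sham, 43 df), and these comparisons are supplementary.

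Finally, the small-sample df can be slightly conservative at N = 24 (0.041 at the lowest in simulation).

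**Conclusion.** The point holds as a conditional gap. If pooling is run without complete-data df, the later-onset ANCOVA intervals would need to be about 7% to 11% wider, and the real two-sided error is about 6.5% to 7.3% rather than 5%. This rests on N = 24, 19 error df, and assumed missing information of 0% to 30%; it is worse where fewer participants contribute.

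The same gap in infantile-onset section 6.1 gives about 5.3% to 5.6% at ranks 1 and 3 to 7. It could matter only for a borderline result at ranks 5 to 7, the 50/28 mg v 12 mg comparisons, where a failure stops all later inference.

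In the unequal-variance sensitivity analysis, the Satterthwaite adjustment would not reach the pooled p-value unless its df are carried into the combination.

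**What to change.** State in later-onset section 5.1.1 and infantile-onset section 6.1 that, for ANCOVA endpoints, PROC MIANALYZE is run with EDF= set to that model's complete-data error df: 19 for later-onset HFMSE at N = 24, 66 for the infantile-onset primary at N = 70, and the matching value for every other model. The value changes with the covariates (HINE Section 2 and NF-L against sham add baseline CHOP INTEND, giving 65 at N = 70) and with the number analysed (PedsQL self-report).

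For the unequal-variance sensitivity analysis, state which df enter the combination, since Satterthwaite df can differ between imputed datasets. Do not extend the rule to the MI logistic regressions, which have no ANCOVA error df.

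The cost is a sentence in each plan, a short table of df by model, and one option in the code. Intervals become slightly wider and p-values slightly larger.
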